1.1.4 Nitric Oxide Synthase and the TIME

We and others have shown that nitric oxide synthase (NOS) expression in the TIME is a powerful driver of tumor-mediated immunosuppression.⁴²⁻⁴⁴ Therefore, TIME-targeting with NOS inhibitors may offer a novel combinatorial approach to enhance anti-PD-1 therapeutic efficacy. Nitric oxide (NO) is a bioactive molecule that exhibits pleiotropic effects within cancer cells and tumors, with concentration-dependent protumor and antitumor effects. NO is produced by three different NOS isoforms: neuronal NOS, inducible NOS (iNOS), and endothelial NOS. The role of iNOS in carcinogenesis, tumor progression, tumor survival, and tumor aggressiveness is well recognized. Increased iNOS expression has been found in various cancers including melanoma, NSCLC, HNSCC, and lymphoma and is associated with poor survival.⁴⁵⁻⁵³ iNOS inhibition has been shown to inhibit melanoma growth *in vivo* and to extend the survival of tumor-bearing mice.⁵⁴ Furthermore, iNOS inhibition enhanced cisplatin-mediated growth inhibition in cisplatin-sensitive and cisplatin-resistant melanoma cell lines *in vitro* and a mouse xenograft model *in vivo*.⁵⁴ NOS inhibition with the pan-NOS inhibitor L-NAME (NG-nitro-L-arginine methyl ester) resulted in a 23% increase in median OS, 33% reduction in tumor volume doubling rate, and 29% reduction in total lung tumor burden in a mouse model of *Kras* mutation-positive NSCLC.⁵⁵ iNOS inhibition has been shown to decrease invasion and enhance the antitumor effect of cisplatin *in vitro* in HNSCC cells.^{56,57} Intratumoral NO and NO-derived molecules induce T-cell dysfunction by negatively impacting T-cell signaling, activation, and migration⁵⁸ and prevent intratumoral infiltration of tumor-specific T-cells.⁵⁹ iNOS is a known effector of MDSC-mediated immune suppression.⁶⁰ In syngeneic mouse melanoma models, iNOS inhibition blocked the intratumoral accumulation of MDSCs, leading to increased recruitment of tumor-infiltrating CD8⁺ T-cells.^{61,62} Furthermore, iNOS inhibition was found to drive macrophages from the immunosuppressive M2 phenotype towards the antitumor M1 phenotype.⁶³ Taken together, these data provide solid evidence of the potential of NOS inhibition to dramatically reshape the TIME to improve the efficacy of anti-PD-1 therapy.

1.1.5 NG-Monomethyl-L-Arginine Preclinical and Clinical Trial Data

We have demonstrated the potent antitumor activity of the pan-NOS inhibitor NG-monomethyl-L-arginine (L-NMMA) against triple negative breast cancer (TNBC) *in vitro* and *in vivo*.⁴² L-NMMA was found to decrease cell proliferation, migration, and mammosphere formation in TNBC cell lines and significantly reduce tumor growth, lung metastases, tumor initiation, and self-renewal in TNBC patient-derived xenografts (PDXs).⁴² Furthermore, L-NMMA in combination with docetaxel significantly inhibited *in vivo* tumor growth compared with docetaxel alone in TNBC xenograft models.⁴² Based on these findings, we have an ongoing Phase Ib clinical trial with proprietary L-NMMA and docetaxel in subjects with relapsed/refractory TNBC (NCT02834403).

The safety of L-NMMA has been well established, and the anticipated SAEs are few, known, and documented.⁶⁴ TRIUMPH was a randomized, controlled Phase III trial of L-NMMA in subjects with acute myocardial infarction and cardiogenic shock. The study was conducted at 130 centers in 8 countries in North America and Europe. Inclusion required all of the following: (1) myocardial infarction, confirmed by ischemic symptoms for at least 30 minutes with elevated cardiac markers and/or ST-segment elevation or left bundle-branch block; (2) patency (<70% stenosis) of the infarct artery, either occurring spontaneously and confirmed at angiography or after percutaneous revascularization; (3) refractory cardiogenic shock of less than 24 hours' duration, confirmed by peripheral signs of tissue hypoperfusion and systolic blood pressure less than 100 mmHg despite vasopressor therapy (dopamine ≥ 7 μ g/kg per minute or norepinephrine or epinephrine ≥ 0.15 μ g/kg per minute) continuing longer than 1 hour after infarct artery patency; (4) clinical or hemodynamic evidence of elevated left ventricular filling pressures; and (5) left ventricular ejection fraction of less than 40%. Hemodynamics and requirement for vasopressor treatment were reconfirmed after randomization just prior to study drug administration; subjects with resolving shock were excluded. Between January 2005 and August 2006, 398 subjects met the study inclusion criteria and were enrolled. All baseline characteristics were well balanced between the treatment groups. More than one quarter of the population was older than 75 years; the majority were male and of white race. More than half of the subjects had hypertension and one third had diabetes; 84 (21%) had a history of heart failure and almost a third of those had advanced heart failure symptoms in the 6 weeks prior to enrollment. A quarter of the subjects had baseline creatinine levels of 1.7 mg/dL (150 μ mol/L) or higher. The median supported blood pressure just prior to study drug administration was 88/52 mmHg. Most subjects were supported with a single vasopressor at the time of study drug administration. The majority of subjects presented with anterior, ST-segment elevation myocardial infarction with left anterior descending infarct artery location. Percutaneous coronary intervention was performed in nearly all subjects to achieve the requirement for less than 70% infarct artery stenosis before study entry. L-NMMA had no effect on mortality in subjects with myocardial infarction complicated by refractory cardiogenic shock. Importantly, L-NMMA was well tolerated with few AEs other than transient (minutes) reversible hypertension. Hemodynamic outcomes and SAEs are shown in Tables 2 and 3, respectively. Subjects who received L-NMMA had a greater increase in systolic blood pressure at 2 hours compared with subjects who received placebo (12.0 mmHg vs. 7.0 mmHg; $P < 0.001$). There were a total of 274 SAEs reported (130 in the placebo group and 144 in the L-NMMA group). No significant differences in safety were noted.

1.2 Rationale

1.2.1 Rationale for the Trial and Selected Subject Population

Pembrolizumab has demonstrated significant clinical activity in patients with melanoma, NSCLC, HNSCC, cHL, urothelial carcinoma, cervical cancer, esophageal cancer, gastric cancer, hepatocellular carcinoma, merkel cell carcinoma, primary mediastinal large B-cell lymphoma, renal cell carcinoma, small cell lung cancer, MSI-H/dMMR cancer, and for the treatment of adult and pediatric patients with unresectable or metastatic tumor mutational burden-high (TMB-H) [≥ 10 mutations/megabase (mut/Mb)] solid tumors, as determined by an FDA-approved test, that have progressed following prior treatment and who have no satisfactory alternative treatment options.. However, a significant proportion of these patients do not respond to or progress after anti-PD-1 therapy, highlighting the need for novel strategies to optimize the efficacy of this therapy. The TIME has emerged as a critical determinant of immune checkpoint inhibitor response, with responses correlated with an immunologically active T-cell-inflamed microenvironment.³⁸ We and others have shown that NOS induces immune dysfunction in the tumor microenvironment.⁴²⁻⁴⁴ Therefore, we hypothesize that NOS inhibition, by targeting the immunosuppressive tumor microenvironment, will reverse resistance to PD-1 blockade and enhance response rates to pembrolizumab in patients with melanoma, NSCLC, HNSCC, cHL, urothelial carcinoma, cervical cancer, esophageal cancer, gastric cancer, hepatocellular carcinoma, merkel cell carcinoma, primary mediastinal large B-cell lymphoma, renal cell carcinoma, small cell lung cancer, MSI-H/dMMR cancer or patients with unresectable or metastatic tumor mutational burden-high (TMB-H) [≥ 10 mutations/megabase (mut/Mb)] solid tumors. We will increase the number of subjects enrolled to 20 subjects to allow for Screen-Fails/withdrawals/deaths. The protocol study population will remain at 12 evaluable subjects.

1.2.2 Rationale for Dose Selection

All subjects will be treated with the recommended dose of pembrolizumab.

L-NMMA will be initially administered at a dose of 15.0 mg/kg. L-NMMA dose will de-escalate (12.5 mg/kg) or escalate (20.0 mg/kg) based on the occurrence of dose-limiting toxicities (DLTs). We previously demonstrated that L-NMMA at a dose of 200 mg/kg was effective in reducing tumor volume in TNBC PDX mouse models.⁴² The 200 mg/kg dose of L-NMMA translates into a 10–15 mg/kg human equivalent dose.⁶⁶ We are currently conducting a Phase Ib/II trial evaluating the safety and efficacy of proprietary L-NMMA at doses ranging from 7.5–20.0 mg/kg in combination with docetaxel in subjects with relapsed/refractory TNBC (NCT02834403).

2.0 OBJECTIVES

2.1 Primary Objective

- To assess the maximum tolerated dose (MTD) of the L-NMMA and pembrolizumab combination in subjects with melanoma, NSCLC, HNSCC, cHL, urothelial carcinoma, cervical cancer, esophageal cancer, gastric cancer, hepatocellular carcinoma, merkel cell carcinoma, primary mediastinal large B-cell lymphoma, renal cell carcinoma, small cell lung cancer, MSI-H/dMMR cancer or for the treatment of adult patients with unresectable or metastatic tumor mutational burden-high (TMB-H) [≥ 10 mutations/megabase (mut/Mb)] solid tumors.

2.2 Secondary Objectives

- To describe the DLTs and other toxicities associated with the L-NMMA and pembrolizumab combination in subjects with melanoma, NSCLC, HNSCC, cHL, urothelial carcinoma, cervical cancer, esophageal cancer, gastric cancer, hepatocellular carcinoma, merkel cell carcinoma, primary mediastinal large B-cell lymphoma, renal cell carcinoma, small cell lung cancer, MSI-H/dMMR cancer, or metastatic tumor mutational burden-high (TMB-H) [≥ 10 mutations/megabase (mut/Mb)] solid tumors, as assessed by the National Cancer Institute Common Terminology Criteria for Adverse Events (NCI CTCAE) v4.03 (see Section 11.1).
- To determine the recommended Phase II dose (RP2D) of the L-NMMA and pembrolizumab combination.
- To evaluate the antitumor activity of the L-NMMA and pembrolizumab combination, as assessed by the Response Evaluation Criteria in Solid Tumors (RECIST) 1.1 (see Sections 7.1.2.6.1 and 11.2).
- To study the plasma pharmacokinetics (PK) and pharmacodynamics of the L-NMMA and pembrolizumab combination.

3.0 ENDPOINTS

3.1 Primary Endpoint

- The primary endpoint will be the identification of the MTD of the L-NMMA and pembrolizumab combination. DLT will be defined as any treatment-related death or any \geq Grade 3 AE (NCI CTCAE v4.03) unless there is clear alternative evidence that the AE was not caused by the trial treatment (see Section 8.0 — Statistical Considerations for a detailed list of DLTs). The DLT assessment window will be defined as the duration required to complete one full cycle of treatment with the L-NMMA and pembrolizumab combination. If treatment is delayed, the timelines for dose escalation and MTD determinations will be adjusted to allow for the completion of the DLT assessment window. Subjects will be considered evaluable for the purpose of establishing dose escalation decisions and the MTD if they satisfy one of the following criteria: receive at least one complete cycle of the L-NMMA and pembrolizumab combination and complete trial assessments without a DLT within the DLT assessment window or experience a DLT within the DLT assessment window and are withdrawn from the trial.

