5.2.1.2 Dose Modification

Pembrolizumab:

AEs (both non-serious and serious) associated with pembrolizumab exposure may represent an immunologic etiology. These AEs may occur shortly after the first dose or several months after the last treatment dose.

Withhold pembrolizumab for any of the following:

- Grade 2 pneumonitis

- Grade 2 or 3 colitis
- Grade 3 or 4 endocrinopathies
- Grade 4 hematological toxicity in subjects with cHL
- Grade 2 nephritis
- AST or ALT > 3 and up to 5 X ULN or total bilirubin > 1.5 and up to 3 X ULN
- Any other severe or Grade 3 treatment-related AE

Resume pembrolizumab in subjects whose AEs recover to Grade 0–1.

Permanently discontinue pembrolizumab for any of the following:

- Any life-threatening AE (excluding endocrinopathies controlled with hormone replacement therapy or hematological toxicity in subjects with cHL)
- Grade 3 or 4 pneumonitis or recurrent pneumonitis of Grade 2 severity
- Grade 3 or 4 nephritis
- AST or ALT > 5 X ULN or total bilirubin > 3 X ULN
 - For subjects with liver metastasis who begin treatment with Grade 2 ALT or AST, if ALT or AST increases by $\geq 50\%$ relative to baseline and lasts for at least 1 week
- Grade 3 or 4 infusion-related reactions
- Inability to reduce corticosteroid dose to 10 mg or less of prednisone or equivalent per day within 12 weeks
- Persistent Grade 2 or 3 AEs (excluding endocrinopathies controlled with hormone replacement therapy) that do not recover to Grade 0–1 within 12 weeks after the last dose of pembrolizumab
- Any severe or Grade 3 treatment-related AE that recurs

L-NMMA:

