Blood pressure will be monitored during L-NMMA infusions. At each L-NMMA infusion, blood pressure will be measured before infusion, 1 hour (± 15 minutes) after infusion start, and at infusion completion. Automatic blood pressure readings will be performed unless manual reading is needed. If systolic blood pressure is >180 mmHg at the 1-hour (± 15 minutes) check, stop the infusion and recheck blood pressure after 15–30 minutes. If blood pressure is not <160 mmHg, recheck blood pressure after another 15–30 minutes. If blood pressure is still not <160 mmHg, the subject is to be discontinued from the trial. The infusion can be resumed in subjects whose blood pressure lowers to <160 mmHg at the first or second recheck. If systolic blood pressure again increases beyond 180 mmHg, the infusion should be stopped and the subject is to be discontinued from the trial. If systolic blood pressure is >180 mmHg at infusion completion, recheck blood pressure after 15–30 minutes. If blood pressure is not <160 mmHg, recheck blood pressure after another 15–30 minutes. If blood pressure is still not <160 mmHg, the subject is to be discontinued from the trial.

Subjects whose treatment is interrupted or permanently discontinued due to an AE including abnormal laboratory value must be followed at least once a week for 4 weeks and subsequently at 4-week intervals until resolution of the event to Grade 1 or better. Dose interruptions should be reported on the appropriate Dosage Administration case report form (CRF). Any AE during Cycle 1 that delays administration of Cycle 2 by more than 7 days will be considered a DLT (see Section 8.0 — Statistical Considerations). The maximum time allowed for toxicity-related treatment interruption for all subsequent cycles is 3 weeks from the intended dosing day. If interruption is > 3 weeks, the subject must be discontinued from the trial treatment. However, the subject will continue to be followed for toxicity.

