The study will utilize the sequential CRM for two-dimensional dose finding method of Yuan and Yin,⁶⁷ a method based entirely on a Bayesian decision framework. The trial is designed to investigate the combination at one dose level of pembrolizumab (200 mg IV Q3W) and 3 dose levels of L-NMMA (12.5, 15.0, and 20.0 mg/kg). The starting dose will be pembrolizumab at 200 mg IV Q3W and L-NMMA at 15.0 mg/kg. The trial will be comprised of 12 subjects and will utilize a standard Bayesian model averaging CRM approach to determine the appropriate dose of L-NMMA. A cohort size of 2 will be used.

The study was designed and will be conducted using Bayesian model averaging CRM software developed by the Biostatistics Department of the University of Texas M. D. Anderson Cancer Center (<https://biostatistics.mdanderson.org/SoftwareDownload/>).^{68,69} The software assumes the probability of toxicity at dose i (π_i) is modeled as $\pi_i = p_i \times \exp(\alpha)$ where p_i is a constant and α is distributed a priori as a normal random variable with mean 0 and variance 2. The software requires the investigator to specify the prior median probability of toxicity at each of the 3 doses of L-NMMA under consideration (s_i , $i = 1, 2, 3$). The CRM model assumes that toxicity is a monotonic increasing function with dose and thus, the s_i values may not decrease as i increases. The values p_i in the probability model are selected so that $E[p_i \times \exp(\alpha)] = s_i$. After the first cohort, each successive cohort is given the dose whose posterior probability of toxicity given the data collected thus far is closest to the target toxicity (the software does not allow an untried dose to be skipped). Thus as information accumulates, the model is continually updated *posteriorly* and decisions are made on the *posterior* distribution. As a result, no data is lost and

there is the assurance that the decision to increase or decrease the dose level is consistently reassessed as more information becomes available. For a dose level to be chosen as the MTD, at least 6 subjects must have received said dose.

Table 8. L-NMMA Dose Escalation

Dose Level	L-NMMA (mg/kg)
-1	12.5
0	15.0
1	20.0

The target toxicity probability will be 0.25 to 0.30 and a maximum of 12 subjects will be treated. The first cohort of subjects will be treated at dose level 0. As an extra measure of safety, the trial will be stopped early if the lowest dose level is unacceptably toxic, formally if

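### The evaluability rule counts a DLT only if the subject is also withdrawn from the trial, so a Grade 3 non-immune DLT can fall out of the CRM, and any resulting bias in the MTD is upward

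*Combined protocol and SAP*

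**What the plan says.** Section 3.1 (Primary Endpoint) gives two routes to being evaluable for escalation decisions and the MTD:

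- (a) "receive at least one complete cycle of the L-NMMA and pembrolizumab combination and complete trial assessments without a DLT within the DLT assessment window"; or
- (b) "experience a DLT within the DLT assessment window and are withdrawn from the trial".

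The window is one cycle: "The DLT assessment window will be defined as the duration required to complete one full cycle of treatment".

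Four other places bear on what happens to a subject with a DLT.

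- **Section 5.2 (Trial Treatment)** allows treatment beyond 3 weeks only for subjects who have had no DLT and no progression.
- **Section 5.2.1.2 (Dose Modification)** withholds pembrolizumab for Grade 3 treatment-related AEs not otherwise listed, and then says "Resume pembrolizumab in subjects whose AEs recover to Grade 0–1". For unresolved blood pressure rises it says "If blood pressure is still not <160 mmHg, the subject is to be discontinued from the trial".
- **Section 5.6 (Withdrawal/Discontinuation)** requires discontinuation from the trial for, among others, Grade 4 or higher AEs, Grade 3 immune-mediated events, a Cycle 1 AE that delays Cycle 2 by more than 7 days, unresolved blood pressure rises, and adverse experiences judged unacceptable. It lists neither a DLT as such nor a non-immune Grade 3 AE.
- **Section 8.0** defines DLTs, including most treatment-related non-hematological AEs of Grade 3 or higher, with no condition about withdrawal.

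On numbers, section 1.2.1 raises enrolment to 20 to allow for screen failures, withdrawals and deaths, and adds "The protocol study population will remain at 12 evaluable subjects". Section 8.0 says "a maximum of 12 subjects will be treated".

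**The concern.** A DLT should enter the dose-finding model because it occurred. Route (b) adds a condition on what happens to the subject afterwards. A subject with a DLT who is not withdrawn fails route (a) because of the DLT and fails route (b) because of staying in. That subject contributes nothing to the CRM, and the allowance of 20 enrolled for 12 evaluable leaves room to replace them.

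A loss of this kind removes only toxic outcomes, so it can act in one direction only: the observed DLT rate is too low, escalation is too easy, and the early stopping rule triggers too seldom. With cohorts of 2 and 12 subjects in all, one missing DLT can change a dose decision. The MTD is the primary endpoint.

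**Working it through.** **1. Which DLTs can be lost?**

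| DLT in Cycle 1 | Named in 5.6 as a reason to leave the trial? | Meets route (b)? |
|---|---|---|
| Treatment-related death | Yes | Yes |
| Grade 4 or higher AE | Yes | Yes |
| Grade 3 immune-mediated event | Yes | Yes |
| AE delaying Cycle 2 by more than 7 days | Yes | Yes |
| Grade 3 non-immune DLT, no such delay | No, unless judged unacceptable | Not assured |

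For the last row, section 5.2 stops trial treatment, while section 5.2.1.2 allows pembrolizumab to resume. Pembrolizumab is given on Day 5 of each cycle, so a resumed dose after a Cycle 1 event would normally fall in a later cycle, which section 5.2 rules out. The two sections conflict, and neither says that the subject is withdrawn from the trial.

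**2. Re-creating the design.** Inputs from section 8.0: doses 12.5, 15.0 and 20.0 mg/kg; start at 15.0; cohorts of 2; maximum 12; α normal with mean 0 and variance 2; the three stated toxicity probability sets; stop if the posterior probability that toxicity at the lowest dose exceeds 0.25 is above 0.80. Assumptions: the power form p_i^exp(α) (the printed product may have lost a superscript), equal prior model weights, posterior-mean averaging, and target 0.25, the end of the stated 0.25 to 0.30 that best matches Table 9. All trial paths were enumerated exactly.

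Against Table 9:

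- Numbers treated agree within 0.1 subject in all 15 cells (Scenario 3: 2.89/4.00/3.53 against 2.9/4.0/3.5).
- The probability of selecting no dose agrees within 2 points in all five scenarios (Scenario 5: 0.77 against 0.75).
- Dose-selection shares do not all agree. For the top dose: Scenario 1, 0.82 against 0.77; Scenario 2, 0.54 against 0.46; Scenario 3, 0.29 against 0.22. The software's final-selection rule is not described, so this is not evidence of an error in Table 9. The re-created figures are best read as changes from their own baseline.

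**3. Effect of losing DLTs.** Let f be the share of DLT subjects treated as non-evaluable and replaced. The protocol gives no value; f = 0, 0.10 and 0.25 are assumptions. A true rate p is then observed as

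p_obs = p(1 − f) / (1 − pf).

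For p = 0.35: f = 0.10 gives 0.315/0.965 = 0.326; f = 0.25 gives 0.2625/0.9125 = 0.288. For p = 0.40: 0.36/0.96 = 0.375 and 0.30/0.90 = 0.333.

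Running the CRM at the observed rates:

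| f | Scenario 3: selects 20.0 mg/kg (true toxicity 0.35) | Scenario 5 (all doses too toxic): stops early |
|---|---|---|
| 0 | 0.29 | 0.77 |
| 0.10 | 0.34 | 0.72 |
| 0.25 | 0.44 | 0.62 |

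**4. One lost event in the first cohort (15.0 mg/kg).**

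- With 1 DLT in 2, the next dose is 12.5. If that subject is dropped and the replacement has no DLT (0 in 2), the next dose is 20.0. This holds at targets 0.25 and 0.30.
- With 2 DLTs in 2, the stopping probability is 0.94, above 0.80, and the trial stops. If one is lost and the replacement has no DLT (1 in 2), it is 0.66 and the trial continues.

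**The case against.** The strongest reply is that the rest of the protocol makes the condition nearly harmless. Section 5.2 ends trial treatment after any DLT. Section 5.6 removes subjects with Grade 4, Grade 3 immune-mediated, long-delay and unacceptable events. Subjects discontinued from the trial under section 5.6 still have safety and disease follow-up, so being followed does not show that a subject was not withdrawn. Section 8.0 attaches no withdrawal condition to a DLT and says that no data is lost. If every DLT subject is regarded as withdrawn, f = 0 and there is no bias. All of this stands, and it confines the problem to the Grade 3 non-immune DLT. It does not remove it: section 3.1 is the only explicit rule on evaluability, and stopping treatment is not stated to be withdrawal.

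Three stronger readings are tempting and are not supported.

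- **That the MTD is biased upward as a matter of course.** The bias is conditional on f, which is unknown.
- **That the protocol shows DLT subjects staying in the trial.** Section 5.2.1.2 does say "the subject must be discontinued from the trial treatment. However, the subject will continue to be followed for toxicity", but this concerns interruptions in cycles after Cycle 1, outside the DLT window.
- **That subjects stopped by toxicity short of a DLT, such as for blood pressure, produce the same bias.** Under the protocol's own definition they are not DLTs. If a share q of all subjects is excluded in this way, the observed rate is p/(1 − q), which is higher than p. In addition, any Cycle 1 AE that delays Cycle 2 by more than 7 days is a DLT whatever its grade, so many such stops may already count. What is missing is a statement of whether that rule covers a Cycle 2 that is never given, and whether a blood pressure stop is itself a DLT.

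**Conclusion.** The point holds in a limited form. As written, section 3.1 can exclude a genuine DLT from the primary analysis. The exposed case is a Grade 3 non-immune DLT in a subject who is not formally withdrawn. Any bias from this exclusion is upward in the selected dose and downward in the chance of stopping.

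If 10% of DLTs were lost, the top-dose selection probability in Scenario 3 would rise by 5 points and Scenario 5 early stopping would fall by 5 points; at 25% the changes are 15 points each. These figures rest on the assumed f, on replacement of lost subjects, and on a re-created CRM whose Scenario 3 baseline (0.29) is above Table 9's 0.22. At f = 0 the effect is nil.

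Two gaps remain beside it. The protocol does not say how a Cycle 1 toxicity stop without a recorded DLT enters the CRM. Its counts of 12 evaluable and at most 12 treated cannot both govern once any treated subject is non-evaluable and replaced.

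**What to change.** 1. In section 3.1, reword route (b) so that any subject with a DLT in the assessment window is evaluable, whether or not that subject remains on treatment or in the trial.
2. State that non-evaluable subjects may be replaced only for reasons unrelated to toxicity.
3. Reconcile the 12 evaluable subjects in section 1.2.1 with the maximum of 12 treated in section 8.0.
4. Reconcile sections 5.2, 5.2.1.2 and 5.6 on what follows a Grade 3 DLT.
5. Reconcile sections 5.2.1.2, 5.6 and 8.0 on how a Cycle 1 toxicity stop enters the CRM, including a blood pressure stop and a Cycle 2 that is never given.

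For items 4 and 5, which clinical rule applies is the sponsor's decision; the need is that it be stated once and consistently.

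The cost is a few sentences, with no change to the model or the planned 12 evaluable subjects. The downside is that the observed DLT rate may be slightly higher.
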